4.10.3.2.2 Incidence of morphological abnormalities

A qualitative interpretation of the ECG will be performed by the cardiologist according to the charter referenced as Standard Banook-Cardiabase Code List. This qualitative interpretation will provide a codification of the abnormalities detected on the recordings according to a code list grouping the abnormalities as:

- Q or Qs pattern
- Axis and Voltage
- Hypertrophy
- ST depression and elevation
- T/U wave abnormalities
- AV conduction
- Intraventricular conduction defects
- Rhythm
- Technical issue
- Overall conclusion

Each single extracted ECG will be analyzed resulting on the description of one or several morphological findings. Each unique finding will be classified according to the charter as normal,

abnormal not clinically significant or abnormal clinically significant. Then a global conclusion will be drawn on the whole ECG as the worst case reported over all findings.

Number and percentage of subjects presenting at least one treatment emergent abnormality, grouped according to the categories defined above, will be computed. The notion of abnormality in this analysis will refer to each individual finding for which the interpretation according to the charter is abnormal (either clinically or not clinically significant) and not ECG global conclusion which can mix normal and abnormal finding for the same ECG.

4.10.3.3 Assay sensitivity

The moxifloxacin C-QTc model will follow the same methods as described for setmelanotide model from Section 4.10.2.1.1 to 4.10.2.1.4. The sensitivity analysis will be performed separately for day 10 and day 16, due to the different baseline for moxifloxacin in group 2 and 3.

The assay sensitivity will be accepted if the slope for the relationship is significant at the 5% level and if the lower bound of the 90% CI of $\Delta\Delta\text{QTc}$ predicted at moxifloxacin C_{max} is above 5 ms.

4.10.4 Pharmacokinetics

4.10.4.1 Pharmacokinetic Concentrations

Setmelanotide and moxifloxacin plasma concentration versus time data will be summarized by treatment group and nominal time using descriptive statistics (number of observations [n], mean, median, CV%, SD, minimum, and maximum). Individual and mean concentration versus time plots will be presented.

Concentration Listings:

Pharmacokinetic concentration data for setmelanotide and moxifloxacin, will be listed by treatment group, and participant for the Safety Population. Concentration listings will include nominal PK sampling time, actual sampling times relative to dose administration, deviation from nominal time, and percent deviation from nominal time, and concentrations. Setmelanotide and moxifloxacin plasma concentrations below the lower limit of quantification (LLOQ) will be presented as below the limit of quantification (BLQ) in the listings and the LLOQ value presented as a footnote. Missing PK samples will be reported as no sample (NS) and/or not reportable (NR) and considered excluded from PK analysis.

Concentration Summary Tables:

Source data as reported from the laboratory will be used for calculation of concentration summary statistics. Tabular summaries for concentration-time data will report N (number of subjects who received treatment), n (number of subjects with non-missing values), and n (BLQ) (the number of subjects with BLQ samples).

Concentration for setmelanotide and moxifloxacin will be summarized by treatment group and nominal timepoint for the Pharmacokinetic Population. The following descriptive statistics will be presented for plasma setmelanotide and moxifloxacin concentrations obtained at each nominal time point: N, n, n(BLQ), arithmetic mean, SD, coefficient of variation (CV%), geometric mean, geometric CV% (calculated as: $g\text{CV\%} = \text{SQRT}(e^{s^2}-1)*100$; where s is the SD of the log-transformed values), median, minimum, and maximum values.

For summary tables, all BLQs will be considered zero, and the number of BLQs and non-BLQs at each scheduled time point will be reported. Summary Statistics will not be calculated if non-BLQ concentrations at a scheduled time point are <3 and will be reported as NC.

The rules followed for calculation and presentation of concentration data with regards to the number of decimal places/significant digits for the listings of participant level concentrations and summary tables of concentration are as follows:

Concentration Listings and Tables	Rounding
Individual concentrations	n s.f. as supplied by bioanalytical laboratory
Minimum and Maximum	n s.f. capped at 4
Mean/SD/Median/Geomean	n+1 s.f. capped at 4
CV%/gCV%	1 d.p.
N/n	Whole number

s.f. = significant figures, d.p. = decimal place

Concentration Figures:

For arithmetic mean linear/linear graphs, all BLQ values will be substituted with zero for calculation of arithmetic mean and for log/linear graphs the log transformed arithmetic mean will be displayed (this should not include zero).

For individual linear/linear and log/linear graphs all BLQ values will be substituted as follows:

- BLQs at the beginning of a participant profile (ie, before the first incidence of a measurable concentration) will be assigned to zero (except for intravenous administration when these BLQs should not be displayed). When using log/linear scale, these timepoints will be considered missing.
- BLQs at the end of a participant profile (ie, after the last incidence of a measurable concentration) will be set to missing.
- Single BLQs which fall between two measurable concentrations will be set to missing.
- Consecutive BLQs which fall between measurable concentrations will be set to missing. Measurable concentrations after consecutive BLQs will be set to missing.

To visualize participant-level concentrations and the comparison between groups for each treatment, the descriptive PK graphs listed below will be generated.

- Figure x.x.x: Individual participant profiles for Setmelanotide Plasma Concentration Time Data – (Linear Scale and Semi-Logarithmic Scale) (Safety Population)
- Figure x.x.x : Overlaid individual participant profiles for Setmelanotide Plasma Concentration Time Data – (Linear Scale and Semi-Logarithmic Scale) (Safety Population)
- Figure x.x.x : Mean (\pm SD) Setmelanotide Plasma Concentration Time Data – (Linear Scale and Semi-Logarithmic Scale) (PK Population)
- Figure x.x.x: Individual participant profiles for Moxifloxacin Plasma Concentration Time Data – (Linear Scale and Semi-Logarithmic Scale) (Safety Population)
- Figure x.x.x : Overlaid individual participant profiles for Moxifloxacin Plasma Concentration Time Data – (Linear Scale and Semi-Logarithmic Scale) (Safety Population)

- Figure x.x.x : Mean (\pm SD) Moxifloxacin Plasma Concentration Time Data – (Linear Scale and Semi-Logarithmic Scale) (PK Population)

Figures will be generated in black and white or color using unique line style and marker for each plot in the graph. For all PK concentration-time plots, linear scale will be used for x-axis (eg, do not use an ordinal scale).

4.10.4.2 Pharmacokinetic Parameters

PK parameters for setmelanotide will be calculated by NCA methods from the concentration-time data using Phoenix® WinNonlin® Version 8.2 or higher following these guidelines:

- Actual time from dose/injection will be used in the calculation of all derived pharmacokinetic parameters, except when parameters are calculated for safety/dose escalation meetings when nominal times may be used to calculate PK parameters.
- There will be no imputation of missing data.
- Handling of BLQ samples for derivation of plasma PK parameters
 - BLQs at the beginning of a participant profile (ie, before the first incidence of a measurable concentration) will be assigned to zero.
 - BLQs at the end of a participant profile (ie, after the last incidence of a measurable concentration) will be set to missing.
 - Single BLQs which fall between two measurable concentrations will be set to missing.
 - Consecutive BLQs which fall between measurable concentrations will be set to missing. Measurable concentrations after consecutive BLQs will also be set to missing.

Pharmacokinetic parameters will be estimated according to the guidelines presented in [Table 4-3](#).

Table 4-3 Pharmacokinetic Parameter and Estimation

Parameter	Guideline for Derivation
C_{max} , t_{max}	Obtained directly from the observed concentration-time data
AUC_{tau}	Area under the plasma concentration-time curve during the dosing interval. If $T_{last} < \tau$ and extrapolation is not possible, AUC_{tau} will be replaced by AUC_{last} under condition that T_{last} is at least 95% of τ .
AUC_{last}	The AUC from zero time (pre-dose) to the time of last quantifiable concentration will be calculated by a combination of linear and logarithmic trapezoidal methods. Unless specifically requested and justified, the linear up/log down trapezoidal method will be employed.
AUC_{0-inf}	The area from zero time extrapolated to infinite time will be calculated as follows: $AUC_{0-inf} = AUC_{last} + \frac{C_{last}}{\lambda_z}$ where C_{last} is the last observed quantifiable concentration.
λ_z	1. The apparent terminal phase rate-constant (λ_z) will be estimated by linear regression of concentration versus time data presented in a log-linear scale. 2. Data are primarily monotonically decreasing in magnitude and are representative of the actual decline in the log concentration-time curve. 3. Only those data points that are judged to describe the terminal log-linear decline will be used in the regression. 4. A minimum number of three data points in the terminal phase will be used in calculating λ_z with the line of regression starting at any post- C_{max} data point (C_{max} should not be part of the regression slope). Unless otherwise determined by PK Scientist's best knowledge and judgment, if the adjusted correlation coefficient (R^2 adjusted) is <0.8 , it will be excluded from the summary tables and statistical analysis of PK parameters, and λ_z and all the λ_z dependent parameters (i.e. $t_{1/2}$, AUC_{0-inf} , CL/F , MRT , and V_z/F) will also be flagged and excluded from summary tables and statistical analysis. The reason for exclusion will be listed/footnoted in parameter listings. In case $0.8 \leq R^2$ adjusted < 0.9 , it will be flagged together with all dependent parameters.

Parameter	Guideline for Derivation
	
5. Unless otherwise determined by PK Scientist's best knowledge and judgment, the interval used to determine λ_z should be equal or greater than 1.5-fold the estimated $t_{1/2}$, and if less than 1.5-fold, λ_z will be flagged in listings and excluded from summary tables and statistical analysis of PK parameters. All the derived parameters (i.e. $t_{1/2}$, $AUC_{0-\infty}$, CL, MRT, and V_z) will also be flagged from listings and excluded from statistical analysis of PK parameters. The reason for exclusion will be listed/footnoted in parameter listings.
 
6. Data points may be dropped from the linear regression if the PK Scientist considers the reported values to be anomalous. Any data points so designated should remain in the listings with a footnote and be identified in the study report with a rationale for exclusion.

CL/F	Apparent clearance of parent drug will be calculated from: $CL/F = \frac{Dose}{AUC_{0-\infty}}$
V_z/F	Apparent volume of distribution at terminal phase may be calculated from: $V_z/F = \frac{Dose}{\lambda_z \times AUC_{0-\tauau}} = (CL/F) / \lambda_z$

PK Parameters Listings:

PK parameters will be listed by participant for the Safety Population. PK parameters that will be excluded from summary tables and statistical analyses of PK parameters will be flagged and footnoted with the reason for exclusion.

PK Parameter Summary Tables:

PK parameters will be provided by CPMS group. Biostatistics group will consider this the PK parameters source data and will use this data without rounding for calculation of PK parameters summary statistics tables.

PK parameters will be summarized by treatment group and for the PK Population.

Tabular summaries for PK parameters will report N (number of subjects who received treatment) and n (number of subjects with non-missing values).

Descriptive statistics for calculated PK parameters will include N, n, arithmetic mean, SD, CV%, geometric mean, median, minimum, and maximum values. For t_{max} , only N, n, median, minimum and maximum values will be presented. No descriptive statistics will be determined when fewer than three individual PK parameters are available.

The rules followed for presentation of PK parameters data with regards to the number of decimal places/significant digits for the listings of participant level PK parameters and summary tables of PK parameters are as follows:

PK Parameter Listings and Tables	Rounding
Derived Individual parameters	4 s.f.
Directly Derived Individual parameters (C_{max})	n s.f. as supplied by the analytical laboratory but not more than 4 s.f.
Minimum and Maximum	4 s.f.
Mean/SD/Median/Geomean	4 s.f.
CV%	1 d.p.
N/n	Whole number
Exceptions for PK Tables	
t_{max} individuals and min/max	2 d.p
t_{max} median only	2 d.p

s.f = significant figures, d.p. = decimal place

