3.2.3 Pharmacokinetic Endpoints

Pharmacokinetic concentration data will be obtained at time point(s) described in the protocol as follows:

Plasma PK concentrations will be determined at the following nominal times: pre-dose, 0.5 (± 2 min), 1 (± 5 min), 1.5 (± 5 min), 2 (± 5 min), 2.5 (± 5 min), 3 (± 10 min), 4 (± 10 min), 5 (± 10 min), 6 (± 10 min), 7 (± 10 min), 8 (± 10 min), 9 (± 10 min), 10 (± 10 min), 12 (± 20 min), 16 (± 20 min) and 24 (± 20 min) hours post-dose

Unless otherwise stated, derivation of PK parameters will be the responsibility of Clinical Pharmacology, Modeling and Simulation (CPMS) group, [REDACTED]

If calculable, the following PK parameters listed in [Table 3-1](#) will be determined for setmelanotide in plasma following repeated SC administration.

Table 3-1 Plasma Pharmacokinetic Parameters after Multiple Dose Administration of Setmelanotide

Parameter	WNL Name	CDISC Name	Definition
Cmax	Cmax	CMAX	Maximum observed concentration in a dosing interval after last dose administration
Tmax	Tmax	TMAX	Time corresponding to occurrence of Cmax after last dose administration
AUCtau	AUC_TAU	AUCTAU	AUC over the dosing interval after last dose administration
AUClast	AUClast	AUCLST	AUC from time zero to the last quantifiable concentration

Parameter	WNL Name	CDISC Name	Definition
Cl/F	CLss_F	CLFTAU	Apparent clearance following oral administration at after last dose administration
Vd/F	Vz_F	VZFTAU	Apparent volume of distribution during terminal phase after last dose administration

If calculable, the following PK parameters listed in [Table 3-2](#) will be determined for moxifloxacin in plasma following single oral administration.

Table 3-2 Plasma Pharmacokinetic Parameters After Single Dose Administration of Moxifloxacin Administration

Parameter	WNL Name	CDISC Name	Definition
Cmax	Cmax	CMAX	Maximum observed concentration
Tmax	Tmax	TMAX	Time corresponding to occurrence of C_{max}
AUClast	AUClast	AUCLST	AUC from time zero to the last quantifiable concentration
AUCinf	AUCINF_obs	AUCIFO	AUC from time zero extrapolated to infinity

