^j Blood samples for quantification of setmelanotide and moxifloxacin concentrations will be collected at pre-dose and 0.5, 1, 1.5, 2, 2.5, 3, 4, 5, 6, 7, 8, 9, 10, 12, 16, and 24 hours post-dose on Days 10 and 16. The PK samples collected at 0.5 hours post-dose will have a sampling window of \pm 2 minutes, samples collected from 1 hour though 2.5 hours post-dose will have a sampling window of \pm 5 minutes, samples collected from 3 hours through 10 hours post-dose will have a sampling window of \pm 10 minutes, and samples collected from 12 through 24 hours postdose will have a sampling window of \pm 20 minutes; however, collection of samples outside of the window will not be considered protocol deviations. The timing of all PK samples should be recorded to the nearest minute. For timepoints at which vital signs, PK blood samples, and/or ECGs are all to be collected, ECGs should be collected first followed by vital signs then PK samples, with the timing of the PK sample to occur at the nominal time.

^k ECGs will be extracted at Day -1 and on Days 10 and 16 at the following timepoints: pre-dose and 0.5, 1, 1.5, 2, 2.5, 3, 4, 5, 6, 7, 8, 9, 10, 12, 16, and 24 hours post-dose. The Day -1 extractions will begin at 7:30 AM (the time of anticipated dosing on Days 10 and 16).

^l For ECG collection, subjects will rest in the supine position for at least 10 minutes before and 5 minutes after each timepoint. For timepoints at which vital, PK blood samples, and/or ECGs are all to be collected, ECGs should be collected first followed by vital signs then PK samples, with the timing of the PK sample to occur at the nominal time.

^m Safety ECGs will be collected at the Screening visit, CRU Baseline (Day -1), final CRU discharge, and the Follow-up visit.

ⁿ Safety clinical laboratory tests will include: hematology with platelet count and standard indices, chemistry panel (includes sodium, potassium, chloride, CO₂, albumin, total protein, glucose, BUN, creatinine, uric acid, AST, ALT, GGT, CPK, alkaline phosphatase, total bilirubin, direct bilirubin, LDH, calcium, phosphorus, magnesium), and urinalysis with microscopic analysis if positive findings on dipsticks warrant further examination. Safety laboratories will also include a coagulation profile (PT or INR, and PTT also referred to as aPTT).

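### SAP Table 4-3 makes setmelanotide CL/F depend by default on the terminal-slope fit, which with 24 h sampling preferentially drops slow eliminators; CL/F should be Dose/AUCtau and not subject to the slope rule

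*SAP*

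**What the plan says.** The slope criteria are in SAP 4.10.4.2, Table 4-3, in the λz row.

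- Item 4: "A minimum number of three data points in the terminal phase will be used", and Cmax is not one of them. If adjusted R² is below 0.8, λz and its dependent parameters, a list that names CL/F, "will also be flagged and excluded from summary tables and statistical analysis".
- Item 5 opens "Unless otherwise determined by PK Scientist's best knowledge and judgment, the interval used to determine" λz, and says that this interval "should be equal or greater than 1.5-fold the estimated" half-life. A λz that fails "will be flagged in listings and excluded from summary tables and statistical analysis of PK parameters". Those words govern λz itself. The derived parameters, a list that names CL, "will also be flagged from listings and excluded from statistical analysis of PK parameters"; summary tables are not mentioned again there.
- Item 4's R² rule carries the same reservation for the PK scientist's judgment.

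Sampling runs from pre-dose through "12, 16, and 24 hours post-dose on Days 10 and 16" (SAP Table 6-1, footnote j).

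The SAP defines setmelanotide clearance in conflicting ways. The CL/F row of Table 4-3 divides dose by AUC0-inf. Table 3-1 (SAP 3.2.3) gives it the names CLss_F and CLFTAU, lists AUCtau as "AUC over the dosing interval after last dose administration", and lists no AUCinf for setmelanotide. The Vz/F row of Table 4-3 equates Dose/(λz × AUCtau) with (CL/F)/λz, which is true only if CL/F is Dose/AUCtau.

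**The concern.** A subject's clearance is removed because the estimated half-life is long relative to the sampling window. Half-life is proportional to V/CL, so low clearance itself makes removal more likely, and the exclusion depends on the quantity being summarised. Cl/F and Vd/F are stated PK endpoints serving the secondary objective on setmelanotide pharmacokinetics (Protocol 4.2 and 5.2.3). By default the CL/F table could describe a faster-clearing subset, while the Cmax and AUCtau tables describe the whole group.

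For this drug the link to λz is also unnecessary. Setmelanotide is sampled over a full once-daily dosing interval, and dosing-interval clearance needs AUCtau, not a terminal slope.

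**Working it through.** The SAP states no figure for the expected loss or bias, so there is none to reproduce.

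**Step 1: which half-lives can pass.** Inputs are the sampling grid (0.5, 1, 1.5, 2, 2.5, 3, 4, 5, 6, 7, 8, 9, 10, 12, 16 and 24 h), the bar on using Cmax, and the factor 1.5. The longest possible regression interval runs from the first sample after Tmax to 24 h, so

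longest admissible half-life = (24 − first sample after Tmax) / 1.5.

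| Tmax (h) | Next sample (h) | Calculation | Longest half-life (h) |
|---|---|---|---|
| 2 | 2.5 | 21.5/1.5 | 14.3 |
| 4 | 5 | 19/1.5 | 12.7 |
| 6 | 7 | 17/1.5 | 11.3 |
| 8 | 9 | 15/1.5 | 10.0 |
| 10 | 12 | 12/1.5 | 8.0 |

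With Tmax at 12 h only the 16 h and 24 h samples remain, fewer than the three points required. Starting the regression later only lowers these limits.

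**Step 2: loss and selection.** The documents give no setmelanotide half-life, Tmax or variability, so these are assumptions: one compartment with first-order absorption; median half-life 4 to 14 h; ka 0.2, 0.4 or 1.0 per hour (median Tmax about 2 to 7 h); CV 30% on CL, V and ka; CL and V uncorrelated; 5% noise. The protocol's 2/3/5/7 mg titration is superposed to Day 16. λz uses all post-Cmax samples, which is lenient to the rule. There are 18 base scenarios of 4,000 subjects each. Selection is the geometric mean of true CL in retained subjects divided by that in all subjects.

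| Half-life (h), ka (/h) | Excluded by default | Selection |
|---|---|---|
| 4, 1.0 | 0.2% | 1.001 |
| 6, 0.4 | 9.6% | 1.037 |
| 8, 0.4 | 26.4% | 1.088 |
| 10, 0.4 | 44.6% | 1.156 |
| 12, 0.4 | 60.4% | 1.215 |
| 14, 0.2 | 90.9% | 1.419 |

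At 10 h and ka 0.4, 0.446 × 20 is about 9 of the 20 evaluable setmelanotide subjects in SAP 4.13. In that scenario selection falls to about 1.015 if half-life varies mainly through V (CV 10% on CL, 40% on V), or if CL and V are correlated at 0.95.

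**Step 3: net error of the reported value.** After repeated dosing, AUC0-inf = AUCtau + Clast/λz, and the second term counts drug left from earlier doses as well as from the last one. Since AUC0-inf exceeds AUCtau, Dose/AUC0-inf is below Dose/AUCtau and understates CL. Relative to true CL:

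| Reported CL/F | Retained subjects, 18 base scenarios |
|---|---|
| Dose/AUC0-inf (Table 4-3 formula) | 0.91 to 1.15, below 1 in 14 of 18 |
| Dose/AUCtau | 1.005 to 1.42 |

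The first row falls to 0.79 when CL and V are correlated at 0.95. At 10 h and ka 0.4, Dose/AUC0-inf gives 0.734 with no exclusions and 0.970 after them, so the two errors partly cancel there.

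**Step 4: after the fix.** Dose/AUCtau with no slope rule loses no subject and gives 1.00 to 1.02 times true CL in all scenarios. A 24 h sample drawn early does not bring the slope back as a condition. The AUCtau row allows AUClast as a substitute from 95% of the interval, 0.95 × 24 = 22.8 h, and the ±20 minute window starts at about 23.7 h.

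**The case against.** The strongest objection is that under Table 4-3's own formula CL/F does depend on λz, so listing it there is coherent. The underlying defect is then the conflict over which clearance is meant. This stands, and it is why the formula and the lists must change together. Deleting CL/F from the lists alone would report clearances built on slopes that the SAP regards as unreliable. Correcting the formula alone would leave items 4 and 5 removing a parameter that no longer needs the slope.

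Other points also stand. The PK scientist can override both criteria, so exclusion is a default and not automatic. For CL, item 5 speaks only of statistical analysis. Since only descriptive PK parameter summaries are planned, removal from them is the likely effect, but for the interval criterion that is an inference. Losses are visible, because N and n are tabulated and reasons footnoted, although n does not show that the loss is selective.

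A reader might infer that the reported CL/F is biased upward. The documents do not support that: only the selection component is upward, and with the written formula the net error was downward in 14 of 18 base scenarios. A reader might also infer that the most exposed subjects drop out of the QT assessment. They do not. They remain in the Cmax and AUCtau summaries, and the C-QTc model uses observed concentrations and geometric mean Cmax, not CL/F.

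**Conclusion.** The point holds as a defect of definition and default exclusion. Items 4 and 5 tie setmelanotide CL/F to the quality of the terminal slope. With sampling to 24 h the interval criterion passes only half-lives up to about 8 to 14 h, and the subjects removed are preferentially slow eliminators. Selection was upward in every scenario tried, from +0.1% to +42%, and about +1.5% where half-life is driven mainly by V or where CL and V are highly correlated. Where in that range the trial would fall cannot be told from the documents; the loss could be negligible or could take most of the group. The net direction under the SAP as written is not established.

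The change is worth making because CL/F is a stated endpoint and the selection is avoidable. The consequence is limited to a descriptive secondary PK summary. No decision rule, primary result or power figure depends on it.

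**What to change.** In SAP Table 4-3:

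1. Define setmelanotide CL/F as Dose/AUCtau, which agrees with Table 3-1 and with the Vz/F row.
2. Delete CL/F from the dependent-parameter list in item 4 and CL from that in item 5, for setmelanotide. No clearance is planned for moxifloxacin (Table 3-2), so nothing changes there.
3. State that CL/F is reported and summarised for every subject with an evaluable AUCtau, whatever the λz fit.
4. Keep the slope criteria for λz, half-life, Vz/F and moxifloxacin AUCinf, which do need the slope. Summaries of these with and without flagged values are optional and not part of this point.

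The cost is SAP wording and the matching derivation in the PK programming. No new data or samples are needed.

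### SAP Table 4-3 computes setmelanotide CL/F as Dose/AUC0-inf on repeat-dose days, which understates clearance and contradicts the Vz/F row and Table 3-1

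*SAP*

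**What the plan says.** SAP section 3.2.3 lists CL/F in Table 3-1, titled "Plasma Pharmacokinetic Parameters after Multiple Dose Administration of Setmelanotide". The row describes it as "Apparent clearance following oral administration at after last dose administration" and gives the output names CLss_F and CLFTAU. Table 3-1 includes AUCtau and AUClast but no AUCinf. AUCinf appears only in Table 3-2, for moxifloxacin, where no clearance is planned. Protocol sections 5.2.3 and 11.3.3 likewise list no AUCinf for setmelanotide.

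The formulas are in SAP section 4.10.4.2, Table 4-3:

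- **AUC0-inf:** "The area from zero time extrapolated to infinite time will be calculated as follows": AUClast + Clast/lambda_z. Nothing is subtracted for drug present before the dose.
- **CL/F:** "Apparent clearance of parent drug will be calculated from" Dose/AUC0-inf.
- **Vz/F:** "Apparent volume of distribution at terminal phase may be calculated from" Dose/(lambda_z x AUC0-tau), which the row equates to (CL/F)/lambda_z.
- **lambda_z, rule 4:** Cmax "should not be part of the regression slope". If adjusted R-squared is below 0.8, lambda_z and its dependent parameters, with CL/F named among them, are excluded from summary tables and statistical analysis.
- **lambda_z, rule 5:** if the regression interval is shorter than 1.5 half-lives, the derived parameters, including clearance, "will also be flagged from listings and excluded from statistical analysis of PK parameters".

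Both rules give way to the PK scientist's judgment. Sampling covers one 24 h dosing interval on Days 10 and 16, after daily dosing from Day 1.

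**The concern.** Dose/AUC0-inf is a single-dose formula. On a repeat-dose day the extrapolated area belongs to that day's dose plus whatever remains from earlier doses, while the numerator counts only that day's dose. The ratio is therefore too small.

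The SAP also points to the other definition. The Vz/F equality is true only if CL/F = Dose/AUCtau, and Table 3-1 provides for AUCtau but not AUCinf. The CL/F that is reported thus depends on which part of the SAP the programmer follows.

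There is a second effect. Using AUC0-inf makes CL/F depend on lambda_z, so the lambda_z quality rules can remove it in subjects whose AUCtau is perfectly usable. Setmelanotide PK is a secondary objective and CL/F is a named PK endpoint.

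**Working it through.** The plan states no clearance value, so there is no figure to reproduce. The check is algebra followed by numbers on the protocol's schedule.

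**Inputs from the documents.** Dosing interval tau = 24 h. Doses are 2 mg on Days 1-7, 3 mg on Days 8-10, 5 mg on Days 11-13 and 7 mg on Days 14-16. The last sample is at 24 h.

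**Assumptions.** Linear PK. The documents give neither half-life nor Tmax for setmelanotide, so a range is shown.

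**Direction.** AUC0-inf on a repeat-dose day = (F x Dose + carry-over)/CL. Hence Dose/AUC0-inf = (CL/F) x F x Dose/(F x Dose + carry-over). This is below CL/F whenever carry-over is above zero, whatever the half-life or absorption rate, and whether or not steady state has been reached.

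**Size at steady state, mono-exponential decline.** Let r = 2^(-24/half-life). Then AUC0-inf/AUCtau = 1/(1 - r), and the understatement is r: 1.6% (4 h), 6.25% (6 h), 12.5% (8 h), 25% (12 h), 50% (24 h).

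**Size on the actual schedule.** Let S = sum of dose_d x r^(day - d) over all doses up to the sampled day. Then AUC0-inf = S/(CL/F) and AUCtau = S(1 - r)/(CL/F).

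Example, Day 10, half-life 12 h, r = 0.25:
- S = 3 x (1 + 0.25 + 0.0625) + 2 x (0.25^3 + ... + 0.25^9) = 3.9375 + 0.0417 = 3.979.
- Dose/AUC0-inf is 3/3.979 = 0.754 of true CL/F, an error of -24.6%.
- Dose/AUCtau is 3/(3.979 x 0.75) = 1.005 of true CL/F, an error of +0.5%.

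Errors on Day 10 / Day 16; the last column adds first-order absorption at an assumed rate of 0.5/h:

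| Assumed half-life | Dose/AUC0-inf, mono-exponential | Dose/AUCtau, mono-exponential | Dose/AUC0-inf, with absorption |
|---|---|---|---|
| 4 h | -1.6 / -1.6% | 0.0 / 0.0% | -2.4 / -2.4% |
| 8 h | -12.4 / -12.5% | +0.1 / +0.1% | -14.7 / -14.7% |
| 12 h | -24.6 / -24.7% | +0.5 / +0.5% | -27.0 / -27.0% |
| 24 h | -47.8 / -47.9% | +4.4 / +4.2% | -49.3 / -49.4% |

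Absorption makes the bias slightly larger. At 1.0/h the error is about -7% (6 h), -26% (12 h) and -48 to -49% (24 h).

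**The Vz/F equality.** If CL/F = Dose/AUC0-inf, the two sides differ by the factor AUC0-inf/AUCtau. With absorption at 0.5/h this is 1.09 (6 h), 1.38 (12 h) and 2.06 (24 h). If CL/F = Dose/AUCtau, they agree exactly.

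**The lambda_z rules.** With Cmax left out of the regression, a peak at an assumed 4 h makes 5 h the first usable sample, and a peak at 8 h makes it 9 h. The 1.5 half-life condition is then met only for half-lives up to (24 - 5)/1.5 = 12.7 h or (24 - 9)/1.5 = 10.0 h. AUCtau is more robust. In footnote j of the schedule, "samples collected from 12 through 24 hours postdose will have a sampling window of" 20 minutes either side. A final sample taken 20 minutes early reaches 23.67/24 = 98.6% of tau, above the 95% that Table 4-3 requires before AUClast may replace AUCtau.

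**The case against.** The main arguments for leaving this alone or rating it lower are these.

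- **The largest figures may never be reported.** Sampling ends at 24 h, so no half-life above 24/1.5 = 16 h can satisfy rule 5, and the 24 h row describes values the SAP restricts. This stands in part. Within the 10.0 h and 12.7 h limits the steady-state bias is 19% to 27%. Read literally, however, rule 5 excludes derived parameters from statistical analysis and does not name summary tables for them, so such values could still be summarised.
- **Bias and loss largely exclude each other.** True for a given subject: a value removed by a rule is not also reported with bias. They are alternative consequences of one formula.
- **The size is unknown.** True. With a short half-life the bias is negligible, and the decimals depend on the absorption model. The direction does not.
- **Table 3-1 gives no denominator.** Reading CLss_F and CLFTAU as Dose/AUCtau relies on naming conventions the SAP does not define. The contradiction does not need them: the Vz/F equality and the absence of AUCinf from the setmelanotide list are enough.
- **Table 4-3 may be template text, and readers could recompute.** It mentions MRT and half-life, which are not planned parameters, and AUCtau and dose are to be listed by participant. That shows why the fix is cheap, not that the formula is sound. If the software reports a steady-state clearance anyway, the output will disagree with the SAP's stated formula.

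**Conclusion.** The concern holds. The CL/F formula in Table 4-3 is wrong for its only use, a repeat-dose profile, and it is inconsistent with the Vz/F row and with the parameters planned in Table 3-1. Given linear PK and some pre-dose drug, the error is always an understatement. Across assumed half-lives of 4 to 24 h it ranges from about 2% to 49%; the true position in that range cannot be fixed from the documents. For half-lives that can pass the 1.5 half-life rule with a 4 h or 8 h peak, it is at most about a quarter of the true value (27% at 12.7 h, 19% at 10 h, at steady state).

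The consequence is confined to descriptive PK: CL/F, and Vz/F if it is derived from CL/F. The concentration-QTc analysis uses concentrations and Cmax and is not touched. This should be corrected before the PK parameters are derived, but it does not threaten the trial's main conclusion.

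**What to change.** In SAP Table 4-3:

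1. Set setmelanotide CL/F = Dose/AUCtau, using the dose actually given on the sampled day. Keep Vz/F = (CL/F)/lambda_z, and reserve AUC0-inf for moxifloxacin.
2. Remove CL/F from the lambda_z-dependent lists in rules 4 and 5, except in subjects whose AUCtau was itself extrapolated with lambda_z.
3. Add a footnote that Dose/AUCtau equals CL/F only at steady state. Each PK day is the third day at its dose level. Protocol section 5.6 allows doses to be delayed or decreased and escalation to be postponed, so flag subjects in whom this happened shortly before a sampled day.

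The cost is one formula, two list edits and one footnote. AUCtau is already calculated, so no new samples or data are needed.
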